Has the participant selection process overprotected potential subjects who are considered vulnerable so that they are denied opportunities to participate in research?

Yes No

4. Number of participants to be included and/or enrolled in this entire study, across all study locations: 1,920 consent cover letters sent; up to 20,000 EHR records

At Utah prior to October 2019: 960 consent cover letters sent; up to 20,000 EHR records

5. Characteristics of Participants/Inclusion Criteria:

Adapted Criteria for Genetic Testing for Inherited Cancer Susceptibilities
First Degree Relative or Second Degree Relative diagnosed with the following regardless of age: Ovarian Cancer, Pancreas Cancer
First Degree Relative or Second Degree Relative diagnosed with the following <50 years of age: Breast Cancer, Colorectal Cancer, Endometrial Cancer
Three or more relatives on the same side of the family diagnosed with the following clusters of cancer regardless of age:
Breast Cancer, Ovarian Cancer, Pancreas Cancer, Prostate Cancer
Colorectal Cancer, Endometrial Cancer, Ovarian Cancer, Pancreas Cancer, urinary tract, brain, small intestine
Melanoma, Pancreas Cancer
Ashkenazi Jewish ancestry and family history of Breast Cancer, Ovarian Cancer, Pancreas Cancer, Prostate Cancer

Inclusion Criteria:

Criteria will be simplified to focus on first- and second-degree relatives, specific cancer type, number of family members, and age at diagnosis (See Table)

The algorithms to stratify patients' risk for this study will be based on National Comprehensive Cancer Network (NCCN) criteria for testing for genes in the homologous DNA repair pathway associated with breast, ovarian, prostate, and pancreas cancer and Lynch syndrome, and international consensus recommendations for genetic testing for hereditary melanoma.

Participants will be eligible to participate if they speak English.

Future possible amendment will to be include Spanish speaking patients.

6. Participant Exclusion Criteria:

Exclusion Criteria:

We will exclude patients who have a prior cancer diagnosis, other than non-melanoma skin cancer, and/or prior genetic counseling or testing related to hereditary cancer.

We will also exclude patients who do not have access to internet and therefore unable to access the patient portal.

7. Is a substantial percentage of the participant population anticipated to be non-English speaking?

Yes No

IRB_00123563

Created: 6/5/2019 3:01 PM

PI: [name]

Submitted: 3/5/2019

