Aim 2 analyses will address the dimensions of Reach, Effectiveness, Adoption, and Implementation from our conceptual framework. For Effectiveness, we will be testing for equivalence between study arms in uptake of genetic testing. We will check randomization by comparing demographic characteristics between patients in the two arms. Any characteristic(s) that are significantly different will be controlled for in the multivariable analysis. We will examine descriptive statistics, and will use Fisher's Exact test with a two-sided 0.05 significance level for univariate comparison of proportions to examine the association between study arm and uptake of genetic testing. We will next build multilevel multivariable logistic regression models to examine the effect of study arm on the outcome controlling for clinic-level (clinic type, patient volume, patient composition, number of providers), provider-level (specialty, years in practice, gender), and patient-level (e.g., sociodemographic, clinical) variables. We will examine the intra-class correlation (ICC) by clinic and provider. If a significant ICC is observed, the regression models will be extended to include random effects for clinic or provider, and fit using software for generalized mixed models. Covariates will be included in models if significant in unadjusted analyses. For Reach, using the multivariable regression models with interaction terms, we will examine whether the effects of study arm on uptake of genetic testing is modified by race/ethnicity or rurality. For Adoption, we will examine the proportions of providers and patients who access educational resources and with referrals, and whether this differs by population subgroup. For Implementation, we will assess responses to patient portal messages and completion of study workflows. Statistical significance will be assessed as $p < 0.05$; SAS 9.4 and/or Stata 15.1 will be used for analysis.

Aim 2 Sample Size

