1. Purpose of the Waiver Request:

Waiver of consent for chart review without patient contact

2. Type of Request:

Waiver of Informed Consent

3. List the identifying information you plan to collect or keep a link to (e.g. names, dates, or identification numbers such as social security numbers or medical record numbers, etc.).

Name and contact information

Demographics

Race/ethnicity

Prior referral to genetic counseling

Family history

Genetic counseling and testing

Primary care provider

Date of last appointment

History of reading and responding to messages via the patient portal

Other health conditions

Identifiers will be deleted from the research record, but we will keep the other information used in planning patient recruitment in order to compare differences between those who did and did not participate in the research questionnaires.

4. Explain why the research could not be practicably conducted without using identifiable information. Examples of such explanation could include the following:

Identifiable information is needed to determine health outcomes in regards to genetic delivery services, in alignment with the research aims.

5. Explain why the research could not practicably be conducted without the waiver or alteration. For example, complete the following sentence "If I had to obtain consent, the research could not be conducted because...":

The investigators would be unable to answer the research question if consent were necessary for chart review without any patient contact. In addition the time for staff to obtain consent to review the EHR would be inefficient for practicable analysis of how genetic delivery impacts primary care.

6. Explain why the research and privacy risk of the research are no more than *minimal*:

Because the review of the patient's electronic health records is specific in data abstraction and will be hosted on secure university servers. Breach of confidentiality is a risk, but minimal and unlikely.

7. Describe the measures you will take to ensure the waiver or alteration will not adversely affect the rights and welfare of the subjects:

The information to be collected is standard of care and research use of such information will not alter care received.

8. Explain how you will, if applicable and appropriate, provide the subjects with additional pertinent information after they have participated in the study, or indicate "Not applicable":

Not applicable

IRB_00123563

Created: 6/5/2019 3:01 PM

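### The Aim 2 uptake model does not prespecify baseline portal use as a covariate, although one arm is delivered through the portal and portal history is a listed EHR item

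*Combined protocol and SAP*

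**What the plan says.** Section 4 (Study Information), item 9, Aim 2 Analysis, describes a multilevel logistic model for uptake of genetic testing, "controlling for clinic-level (clinic type, patient volume, patient composition, number of providers), provider-level (specialty, years in practice, gender"), "and patient-level (e.g., sociodemographic, clinical) variables". Entry into the model is conditional: "Covariates will be included in models if significant in unadjusted analyses".

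The same paragraph has a separate rule for imbalance. "We will check randomization by comparing demographic characteristics between patients in the two arms", and "Any characteristic(s) that are significantly different will be controlled for in the multivariable analysis". Responses to portal messages appear there only as an Implementation outcome.

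The EHR data lists in the Request for Waiver of Consent (item 3) and the Request for Waiver of Authorization (item 3) include "History of reading and responding to messages via the patient portal" and "Prior referral to genetic counseling", both at patient level. Section 4, item 6, Patient Screening, already distinguishes patients with no portal account and patients not actively using one at the time of contact. Section 3, item 6, excludes patients with "prior genetic counseling or testing related to hereditary cancer".

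**The concern.** The patient-directed arm receives its education, test offer and negative results through the portal, and in both arms the first notice goes by portal message where the patient has an account. Whether a patient was using the portal beforehand is therefore a plausible predictor of uptake, and the trial lists the raw item for collection. It is not named in the outcome model. Because it is not a demographic characteristic, an imbalance in it would not trigger the imbalance rule. Naming it would not be enough either, because a listed covariate can still be dropped by the unadjusted significance screen.

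A second candidate acts at clinic level: how much each clinic's patients were already using genetic services before the trial. With 48 clinics in the sample-size calculation, 16 of them in the enhanced arm, differences between clinics carry much of the uncertainty in the arm contrast. At stake is the width of the interval judged against the ±0.10 equivalence margin.

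**Working it through.** **Inputs.** From Aim 2 Sample Size: 32 clinics of 15 and 16 clinics of 30 (480 per arm), ICC 0.05, margin ±0.10, significance level 0.05 (taken as two one-sided tests), stated power 80%. Not in the documents: expected uptake, and the strength of association of either covariate with uptake.

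**1. The plan's own figure.** With true difference 0, power = 2Φ(0.10/SE − 1.645) − 1. Design effects are 1 + 14 × 0.05 = 1.70 and 1 + 29 × 0.05 = 2.45, so SE² = p(1−p)(1.70 + 2.45)/480 = 0.00865 p(1−p). Since p is not given, 80% cannot be uniquely reproduced. It is met at p of about 16.1% (SE 0.0342), or 15.6% with the Farrington-Manning variance. At p = 30% the same formula gives 51.7%.

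**2. Where the variance lies**, in units of p(1−p):
- between clinics: 0.05 × (1/32 + 1/16) = 0.0047
- within clinics: 0.95 × (2/480) = 0.0040
- between-clinic share: 0.0047/0.0086 = 54%, whatever the uptake.

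At p = 16% the clinic SD is √(0.05 × 0.16 × 0.84) = 0.082. Clinic effects alone then give a chance arm difference with SD 0.082 × √(1/32 + 1/16) = 0.025, or 2.5 points against a 10-point margin.

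**3. Possible gain if some between-clinic variance is explained** (share R² assumed, p = 16.1%):

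| R² | SE | Power |
|---|---|---|
| 0 | 0.0342 | 80.0% |
| 10% | 0.0332 | 82.8% |
| 25% | 0.0318 | 86.7% |
| 50% | 0.0292 | 92.5% |

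**4. The clinic prior-use rate, measured with error.** Simulation of 3,000 trials per setting used p = 16%, 960 patients, 100-400 flagged patients per clinic, and correlation r between a clinic's prior rate and its trial uptake:
- r = 0.3: variance falls 1-3%
- r = 0.5: falls 8-11%; power goes from about 78-79% to 82-83%
- r = 0.7: falls about 20%; power goes from about 79% to 87-90%
- r = 0: one to two points of power are lost.

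These gains are smaller than step 3 implies at R² = r², because the rate is estimated with error and costs a degree of freedom. The upper cluster size reflects 20,000/48 ≈ 417, where 20,000 is a ceiling in the documents.

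**5. Portal status.** No gain was computed. The documents give neither its distribution nor its relation to uptake.

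**The case against.** Several points on the other side stand.

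- The patient-level list is introduced as examples and patient composition is undefined. Portal status is unspecified, not ruled out. Item 9 asks only for a summary of methods, and the opening page says the full protocol is published elsewhere; that publication is not available here.
- A reader might infer that the trial already holds each clinic's prior genetic-services rate. The documents do not say so. The lists are patient-level, the numerator would include patients whom the trial excludes, and the stated reason for keeping the data is to compare questionnaire participants with non-participants. The rate is derivable only if screening records are kept by clinic.
- That rate is not a true baseline of the outcome. Prior use reflects routine referral, whereas trial uptake follows automated identification and outreach among patients without prior counseling or testing. Even the sign of the correlation is uncertain. Prior use may also be rare: the Background cites 2.7% tested among unaffected women with a family history. With clinic rates near that level and an assumed baseline ICC of 0.01, simulation (2,000 trials) gives variance reductions of about 10% at r = 0.7 and 4% at r = 0.5 with 100 patients per clinic, and 18% and 7% with 400.
- The calculation above uses 960 patients, but the plan enrolls 1,920. With 30 and 60 per clinic in the same 48 clinics, ICC 0.05 and 16% uptake, power is already about 91% unadjusted. It would be about 93% at r = 0.3 and 96% at r = 0.5 with perfect measurement. At 30% uptake it starts near 70%. The plan also calls ICC 0.05 a likely overestimate, and a lower value shrinks the clinic-level gain.

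None of this removes the case for prespecifying portal status: the raw item is to be collected, and neither the significance screen nor the demographic check secures its use.

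**Conclusion.** The point holds as a low-cost improvement of unknown size. Baseline portal use is not named for the uptake model, and the rules as written would not guarantee adjustment for it. The clinic prior-use rate is a weaker, optional candidate. Its gain runs from a small loss of power to about 20% of variance, depending on an uptake and a correlation that the documents do not give.

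A reader might go further and say that chance clinic imbalance stays uncorrected or that the result is biased. The documents do not support that. The listed clinic and provider covariates, the demographic rule and the conditional clinic random effect deal with part of it. Imbalance on these two variables is not specifically corrected, and chance imbalance does not bias a randomised contrast on average. Nor can a definite loss of precision be claimed, since a covariate that predicts nothing brings no gain.

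**What to change.** In the Aim 2 model, prespecify each patient's portal status before the first study notification (active, inactive, none) and include it regardless of significance. State the cut-off and use no message data from after notification, since later message activity can be affected by the arm. The data lists give no such window, so the SAP must supply it. Report the standardised risk difference from this model against the ±0.10 margin, because logistic coefficients are not on the margin's scale.

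Optionally, as a secondary or sensitivity covariate, add each clinic's proportion of criteria-meeting patients with a genetics referral, counseling or testing recorded before the first notification in that clinic, if screening records allow it.

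The cost is SAP wording, a dated extract of portal status and, for the option, one EHR tabulation and one clinic-level degree of freedom. The continuing review submitted in January 2024 reports that analysis of primary outcomes was under way. If outcomes by arm have already been seen, report the adjusted model as a sensitivity analysis.

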PROTOCOL TITLE: Broadening the Reach, Impact, and Delivery of Genetic Services (BRIDGE)

NCT NUMBER: NCT03985852

PROTOCOL DATE: 06/05/2019

The full trial protocol is available at:

[name], [name], [name], et al. Comparing models of delivery for cancer genetic services among patients receiving primary care who meet criteria for genetic evaluation in two healthcare systems: BRIDGE randomized controlled trial. *BMC Health Sciences Research*. 2021;21:542. doi:10.1186/s12913-021-06489-y

Date: Tuesday, August 6, 2024 10:49:19 AM

[Print](#)[Close](#)**IRB_00123563****Created:** 6/5/2019 3:01 PM**PI:** [name]**Submitted:** 3/5/2019**Title:** Broadening the Reach, Impact, and Delivery of Genetic Services**IRB_00123563**

1. Contacts and Title

1. Study Introduction

1. Responsible Investigator:

[name]

Email	Training	Col Date
[contact]	4/25/2022 SMCG	3/19/2024

a. Position of the Investigator:

Faculty or Non-Academic Equivalent

Student

Staff

Resident/Fellow

Other

2. Contact Persons for the Responsible Investigator:

Name	Email	Training
[name]	[contact]	2/22/2023 MCG
[name]	[contact]	3/4/2024 SMCG
[name]	[contact]	3/21/2022 SMCG
[name]	[contact]	1/9/2023 SMCG

3. Guests of the Responsible Investigator:

Last Name	First Name	E-Mail
[name]	[contact]
[name]	[contact]
[name]	[contact]
[name]	[contact]
[name]	[contact]

4. What type of application is being submitted?

New Study Application (or Amendment/Continuing Review)

5. Title Of Study:

Broadening the Reach, Impact, and Delivery of Genetic Services

6. Study Purposes and Objectives:

The proposed study will employ an implementation science framework to compare two models of genetic services delivery for 1,920 patients in a randomized controlled trial with clinic-level randomization. We hypothesize that uptake of genetic testing (Study Aim 2) and adherence to management recommendations (Study Aim 3) will be equivalent between the genetic services delivery models. We propose the following Specific Aims:

Aim 1) Identify primary care patients who qualify for genetic risk assessment in two healthcare systems using a CDS infrastructure to automatically evaluate family history.

*This aim has already been studied in IRB #105797. We will be utilizing this tool that is now available. Aim 1 will not be analyzed in this protocol but is part of our overall research model.

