Research Aims to be studied in this protocol:

Aim 2) Compare uptake of genetic testing for patient-directed standard of care vs. enhanced standard of care genetic services delivery models for 1,920 unaffected primary care patients. We will utilize a randomized trial design with clinic-level randomization to compare two standard of care models: a *patient-directed standard of care* model and an *enhanced* model. In the *patient-directed* model those identified by the clinical decision support (CDS) infrastructure as meeting testing criteria will be informed of their cancer risks, provided with educational resources, and offered the option to select genetic testing through a patient portal. This online portal will be overseen by HCI genetic counselors. The *enhanced standard of care* model in which primary care providers and patients are notified through CDS when criteria are met (the *enhancement* of standard of care) and of the availability of standard of care genetic services. We will compare uptake of genetic testing by model and by race/ethnicity and rurality.

Aim 3) Compare adherence to recommendations and other patient responses for the genetic services delivery models. We will compare the effects of the genetic services delivery models on adherence to management recommendations at 12 months after return of results, or last genetic services contact. We will assess cognitive (i.e., recall, comprehension, uncertainty, risk perceptions) and affective (i.e., test-related distress, positive reactions, decision regret) responses at 4 weeks, and communication (i.e., family, provider) interactions at 4 weeks and 12 months after last genetic services contact. We will also examine differences in effects by race/ethnicity and rurality.

7. Is this a multi-site study, where more than one site needs IRB approval?

Yes No

8. Background and Introduction:

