Research Procedures

1. A research coordinator or genetic counseling assistant will determine who is eligible to participate in the research procedures based on participation in genetic services and access to MyChart, the patient portal. A waiver of recruitment is being requested for this authorization. Up to 20,000 unique electronic health records may be accessed to determine inclusion in this study, and basic health outcomes tracked for comparison.
2. Consent cover letter will be sent via patient portal to offer participation in this research study, with a link to an online questionnaire. The consent cover letter will be sent to patients approximately 4 weeks after genetic test results are returned for those who decide to test and about 8 weeks after participation in pre-test genetic counseling services for those who decide not to test.

If no response is received to the first message, after 1 week another message in the patient portal will be sent. If still no response up to 3 phone calls will be made.

3. Online questionnaires will utilize REDCap, which has a HIPAA-compliant interface. Estimated 960 patients will be offered participation through University of Utah Health; 1,960 patients over both participating sites.

i. **Questionnaire #1:** At about **4 weeks after return of results for those who decide to test** (8 weeks after pre-test genetic counseling), we will assess cognitive (i.e., recall, comprehension, uncertainty, risk perceptions), affective (i.e., test-related distress, positive reactions, decision regret), communication (i.e., family, provider) responses, experience with genetic counseling, and sociodemographic characteristics including numeracy for those who decide to test. For those who do not decide to test, we will assess experience with genetic counseling, reason for not testing, decision regret, risk perceptions, and sociodemographic characteristics including numeracy.

ii. **Questionnaire #2:** At about **12 months**, we will ask about discussion of their test results with their PCP, family members, or others, and self-reported use of cancer screenings for those who decide to test. We will also utilize EHR data to examine adherence to recommendations. For those who decide not to receive genetic testing, we will assess the self-reported use of cancer screenings, whether genetic testing was pursued at another time or through another source, communication with family members and whether other relatives had testing.

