- **What results (preliminary or final) have been obtained from the study? If the study is part of a multi-center trial, this should be stated and any available results provided. If there are no results that are appropriate to report to the IRB at this time, this should be stated and explained:**

We are working on analysis of primary trial outcomes and anticipate having those ready in 2024.

Please attach any abstracts or publications:

Name Version Date Created Date Modified Date Approved

There are no items to display

- **Describe participant enrollment and its effect on the study design and scientific merit. If under-accredd, describe any plans for increasing enrollment during the next approval period. If a multicenter trial, also discuss enrollment at other sites.**

As in the approved protocol and consistent with the last continuing review, we are counting enrollment as those who completed questionnaire 1 or questionnaire 2 as those are the research procedures for this study. There are some participants at the NYU site who may still complete questionnaire 2, which is why the study is left open for enrollment at this time.

The negative number above in the enrolled at all sites comes from the discrepancy in the correction in last year's reporting of enrolled numbers and the continuation of counting only participants who complete research activities. Our accrual numbers to date are 237 at Utah and 98 at NYU, leading to the 335 reported above. In the last approved CR, we reported accrual of 307 but we are not able to indicate that in the fields above.

IRB_00115509 - CR_12/15/2023 4:09 PM

Created: 12/15/2023 4:09 PM

PI: [name]

Submitted: 1/4/2024

Title: Broadening the Reach, Impact, and Delivery of Genetic Services

HELP?

Progress of Sites and Enrollment

Select each site to update the enrollment information.

List of Study Controlled Locations

	Site Name	Investigator's Name	Enrollments since Last CR	Enrollments as of Today	Non English Speakers	Withdrawn
View	NYU School of Medicine	[name]	27	98	0	0
View	University of Utah	[name]	1	237	2	0

IRB_00115509 - CR_12/15/2023 4:09 PM

Created: 12/15/2023 4:09 PM

PI: [name]

Submitted: 1/4/2024

Title: Broadening the Reach, Impact, and Delivery of Genetic Services

HELP?

3. Problems & Events

Provide narrative summary of any available information regarding adverse events which**1. have occurred since the last IRB review.**

- no events to report

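### Health system is not named in the regression models of a clinic-randomised trial run in two systems, which costs precision and leaves any chance imbalance between systems uncorrected

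*Combined protocol and SAP*

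**What the plan says.** Aim 1 places the work in two systems: "Identify primary care patients who qualify for genetic risk assessment in two healthcare systems". The Aim 2 design is stated as "We will utilize a randomized trial design with clinic-level randomization". The text supplied does not say whether clinics were stratified by system.

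Under section 4 (Study Information), item 9, Aim 2 Analysis, the multilevel logistic model is described as "controlling for clinic-level (clinic type, patient volume, patient composition, number of providers", followed by "provider-level (specialty, years in practice, gender), and patient-level (e.g., sociodemographic, clinical) variables". The selection rule is "Covariates will be included in models if significant in unadjusted analyses". System is also absent from the balance check (patient demographics), the random effects (clinic or provider, added only if the ICC is significant), the planned interactions (race/ethnicity, rurality) and the sample size. Aim 3 Analysis refers back to the same model-building procedure.

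Aim 2 Sample Size plans 480 patients per arm, from 32 clinics of 15 (patient-directed) and 16 clinics of 30 (enhanced), with a margin of ±0.10, ICC 0.05, alpha 0.05 and 80% power.

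**The concern.** System is a main structural feature of this design: every clinic belongs to one of two systems. Without a system term, a difference in testing uptake between systems is counted as ordinary clinic-to-clinic variation. Equivalence is decided by whether an interval fits inside ±10 points, so extra variance counts directly against the trial's main claim.

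The selection rule does not secure the adjustment. Even if system were offered as a candidate, a significance screen would decide whether it stayed. That would leave the handling of a design factor to the data.

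**Working it through.** **Inputs from the plan.** n = 480 per arm; cluster sizes 15 and 30; ICC 0.05; margin 0.10; alpha 0.05 one-sided for each of two tests; 48 clinics, 32 against 16.

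**Assumed, because the documents do not give them.** Uptake p, the between-system gap d, and the clinics per system. I take 24 clinics per system. Research Procedures supports roughly equal halves of patients ("Estimated 960 patients will be offered participation through University of Utah Health; 1,960 patients over both participating sites"; the total is 1,920 elsewhere), but gives no clinic counts.

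**Step 1: the plan's own power.** Design effects are 1 + 14 × 0.05 = 1.70 and 1 + 29 × 0.05 = 2.45. With true difference zero,

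SE² = p(1−p)(1.70 + 2.45)/480; power = 2Φ(0.10/SE − 1.645) − 1.

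No uptake proportion is stated, so the 80% cannot be checked outright. It reproduces at p ≈ 0.16: SE = √(0.1344 × 4.15/480) = 0.0341, power 0.80. I use p = 0.16 below.

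**Step 2: what a system gap adds to the ICC.** With half the clinics in each system, the gap adds (d/2)² to the between-clinic variance, so its ICC contribution is (d/2)²/[p(1−p)]. For d = 0.08: 0.0016/0.1344 = 0.012.

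**Step 3: power.** There are two ways to read the planned 0.05.

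- *It includes system variation.* Adjusting removes 0.012, leaving 0.038. Design effects are 1.53 and 2.10, SE 0.0319, power 86% against 80%.
- *It is the within-system value.* Omission raises the working ICC to 0.062. Design effects are 1.87 and 2.80, SE 0.0361, power 74% against 80%.

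| Assumed gap | ICC contribution | Power without system term, if 0.05 is within-system | SD of chance shift, unstratified |
|---|---|---|---|
| 5 points | 0.005 | 78% | 0.8 points |
| 8 points (20% v 12%) | 0.012 | 74% | 1.2 points |
| 16 points (24% v 8%) | 0.048 | 55% | 2.5 points |

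The 16-point row is an extreme case.

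**Step 4: chance imbalance without stratification.** If k of one system's 24 clinics fall among the 32 patient-directed clinics, the between-arm difference in that system's share is k/32 − (24−k)/16. Under the hypergeometric distribution its mean is 0 and its SD 0.155. The shift in the arm contrast is d times this; for d = 0.08 the SD is 0.155 × 8 = 1.2 points. The share difference moves in steps of 3/32. An absolute value of at least 0.281 has probability 12.5%, and a larger one about 3%. So with an 8-point gap, 12.5% of allocations reach 2.25 points (0.281 × 8) and about 3% exceed it.

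**Step 5: the shift and the ICC increase are one quantity.** System variance 0.0016 × (1/32 + 1/16) × 48/47 gives √0.000153 = 0.0124, or 1.2 points, which is the SD in step 4. They must not be added together.

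**The case against.** A reader might infer that the omission biases the arm contrast. The documents do not support that. If clinics in both systems had the same chance of each arm, the expected shift is zero, and a model with clinic random effects already carries the chance shift in its standard error. If randomisation was stratified, omitting the stratum makes the interval conservative. Systematic bias needs an allocation ratio that differs by system; the 32/16 split is a sample-size input and nothing says how it divides by system. The rule that adds clinic effects only when the ICC is significant could undermine the standard error, but that is a separate matter.

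A reader might also take "Our accrual numbers to date are 237 at Utah and 98 at NYU", in the continuing review created 12/15/2023, as evidence that uptake differs. Those counts are people who completed questionnaire 1 or 2, not people tested. The preceding year's review reports similar Questionnaire 1 invitations: about 450 at Utah and 480 at NYU. The counts do show that the questionnaire sample is mostly from one system (237/335 = 71%), which bears on Aim 3 but does not measure the Aim 2 gap.

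Three further objections stand in part:

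- **Planned power may not be lost.** If 0.05 already includes system variation, adjusting is a gain rather than a repair, and the plan calls 0.05 a likely overestimate. The plan also enrols 1,920. At 960 per arm in the same 48 clinics (clusters of 30 and 60), the formula gives 91% at ICC 0.05 and 85% at 0.062; only the 16-point case falls below 80%, to about 66%.
- **Other covariates may act as proxies.** Clinic type, patient composition and sociodemographic variables could absorb part of a system difference. They face the same significance screen.
- **The text is a summary.** It points to a published full protocol that may describe stratification. If it does, the model should still carry that factor.

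**Conclusion.** The point holds as one about precision and chance imbalance in the regression models; it does not show that the comparison is biased. Its size depends on a between-system uptake gap that the documents do not report. Under the stated assumptions, an 8-point gap is worth about 6 points of power on either reading of the ICC, while a 5-point gap costs about 2.5. No magnitude can be given for Aim 3. The recommendation is worth making because the term is nearly free and because a structural design factor should not depend on a significance screen.

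**What to change.** In the Aim 2 and Aim 3 analysis text, specify health system as a fixed effect in the regression models, kept regardless of significance. Base the arm conclusion on those models, for Aim 2 as a difference in proportions because the margin is on that scale. Fisher's exact, t and Wilcoxon tests cannot carry a system term and should be labelled as unadjusted description. Report the arm difference within each system descriptively. State whether randomisation was stratified by system, and give clinic counts by arm within each system.

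The cost is one degree of freedom from 48 clinics, a short addition to the analysis text, and a change in which analysis supports the conclusion. No new data are needed.
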